7.2 Methods, terms of assessment, registration and analysis of efficiency parameters

Calculation of urination episodes number and urinary incontinence episodes number will be performed on basis of data recorded by patients into their diaries.

Mean daily number of urination episodes is calculated as total number of episodes during the day (from 7 am to 7 am of the next day) for the study period (between visits) divided into number of days in period.

Average daily number of incontinence episodes is calculated the same way.

Mean daytime number of urinary incontinence episodes is calculated as total number of episodes during the period from 7 am to 11 pm for the study period (between visits) divided into number of days in period.

Mean nighttime number of urinary incontinence episodes is calculated as total number of episodes during the period from 11 pm to 7 am for the study period (between visits) divided into number of days in period.

Mean number of urinary incontinence episodes per week is calculated as total number of episodes during the study period (between visits) divided into number of days in period.

During randomization visit, treatment visits (Visits 3, 4, 5) and end of treatment visit (Visit 6) investigator will summon diary from patient, verify comprehensives of its filling, record results in CRF with further automatic calculation of mean values.

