4 STUDY DESIGN

4.1 Study endpoints/efficiency criteria

Primary efficiency criteria:

Change of mean daily number of urination episodes at the 12 week Visit against the Visit of starting therapy.

Secondary efficiency criteria:

1. Change of mean daily number of urinary incontinence episodes at the 12 week Visit against the Visit of starting therapy.
2. Change of mean daily number of urinary incontinence episodes during daytime (from 7 am to 11 pm) at the 12 week Visit against the Visit of starting therapy.
3. Change of mean daily number of urinary incontinence episodes during nighttime (from 11 pm to 7 am) at the 12 week Visit against the Visit of starting therapy.
4. Change of mean daily, mean daytime and mean nighttime number of urinary incontinence episodes at the weeks 2, 4, 8 Visits against the Visit of starting therapy.
5. Change of mean number of urinary incontinence episodes per week at the 12 week Visit against the Visit of starting therapy.
6. Change of mean daily number of urinary incontinence episodes at the weeks 2, 4, 8 Visits against the Visit of starting therapy.
7. Changes in overactive bladder symptoms assessment parameters according to Overactive bladder Awareness Tool Questionnaire at Visits 2, 4, 8 and 12 weeks in comparison to the visit before the beginning of therapy.
8. Change of quality of life assessment using EQ-5D questionnaire (at the 12 week Visit against the Visit of starting therapy).

4.2 Justification and brief description of the study design.

[figure not shown]
International multicentral (performed in several research centers within the territory of Russian Federation and Belarus Republic), open-label, randomized comparative (parallel-group) efficiency and safety clinical study, where patients group, taking medicinal product Uritos[®] (Imidafenacin), is considered to be test group, and group, taking medicinal product Urotol (tolterodine) is considered to be active control group (comparator product group). Non-inferiority assessment study.

No more than 350 patients are planned to be screened and 300 patients are planned to be randomized (150 per study group), that, with due consideration of assumed withdrawal during treatment period, will give at least 222 patients completely finished the study (111 patients per study group).

Parallel study design was selected in scientific purposes.

Study design is presented on the Figure 1. and detailed description is presented in the Section 4.5.3.

Fig. 1 Study scheme

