4.5.3.1 Visit 1 (Screening): Days from -14 to -1

Screening period should not exceed 14 days before randomization visit/beginning of therapy.

During the screening patient’s conformity towards inclusion/non-inclusion criteria is verified.

During screening visit following receipt of informed consent from the patient acquisition of baseline information of the patient, including demographic data (sex, date of birth, race, body mass, height), medical anamnesis, diagnosis, concomitant pathology and previous and concomitant therapy with designated date of start of product administration and doses within 30

days before screening visit; for female and male patients – birth control methods, for female patients – terms of menopause beginning.

Patient fills out OAB Awareness Tool Questionnaire for assessment of overactive bladder symptoms severity.

Physical examination with BP and HR assessment is performed.

Assessment and registration of adverse events starts from the moment of signing of informed consent form.

Clinical and biochemical blood tests (ALT, AST, bilirubin, creatinine, total protein, glucose, alkaline phosphatase, cholesterol, potassium, sodium) and urinalysis will be performed in the central laboratory. Serological examination for HIV, hepatitis B and hepatitis C is performed. Moreover, PSA testing is performed in male patients.

US-examination of kidneys, bladder and urine excretory ways with residual urine volume assessment is performed for exclusion of bladder structural pathology.

Cough probe is performed for assessment of urethral sphincter capability in women.

12-lead ECG is performed.

Female patients of childbearing potential undertake pregnancy test using dipstick (in the research center).

- All patients should be discussed with efficient birth control issues:

Female patients of childbearing potential and male patients and their female partners should use at least two birth control methods, one of those is barrier, including double barrier contraception method (condom in combination with intravaginal spermicide, cervical caps with spermicide, diaphragms with spermicide) during the whole study period and at least 30 days following administration of the last dose of the study product. Moreover, in addition to barrier contraception method, female patients of childbearing potential may use other approved birth control method:

- Oral, transdermal, implantational and injectional hormonal therapy;
- Intrauterine device (IUD).

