6.3 Measures for control over patients' compliance with study procedures

Compliance assessment will be performed by diary where patient should record data concerning product receipt, as well as be control of amount of product, issued at visits 2, 3, 5 and 5 and returned at visits 3, 4, 5 and 6.

Before participation in the study patients will be informed about risks and restrictions associated with the study. Investigator possesses the right to deny patient's participation in the study in case of his/her suspicion of further study procedures violation from the patient's side.

Compliance will be calculated according to the following formula:

$$K (\%) = N (\text{actual administrations}) / N(\text{scheduled administrations}) \times 100\%.$$

Compliance not lower than 95% will be considered as satisfactory.

Control over compliance will be performed by the diary records.

Patient's diary will be issued to patients not only for assessment of efficiency endpoints, but also for additional control over investigation procedures compliance. Diary, among OAB symptoms (number of urinations, incontinence episodes, micturition urgency) should include information concerning administration of the study product and any adverse events. Patient should take his diary with him/her for each visit. Investigator checks regularity and accuracy of diary filling by the patient. When necessary patients can be instructed repeatedly concerning diary filling rules.

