9.5 Accounting procedures for missing, non-assessable and equivocal data

Missing, non-assessable and equivocal data will not be substituted and considered to the frames of statistical analysis of the results. All missing or equivocal data as well as data, not included into statistical analysis, will be registered according to CRO procedures. All data unaccounted during analysis will be described and justified in final study report.

Before taking decision concerning inclusion of data, obtained during clinical study, into assessment, patients compliance will be evaluated.

Following indicators will be applied:

Taking Compliance (CC) reflects relationship between number of the product doses taken within defined period and doses, prescribed by attending physician.

Formula: TC = number of doses taken: number of prescribed doses x 100%.

Timing Compliance (TiC).

Formula: TC = number of doses taken in the right time: number of prescribed doses x 100%.

Data would not be taken into consideration when “Product receiving compliance” indicator is less than 90%, and “Accuracy compliance” is less than 90%.

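### Section 7.2 keeps blank diary days in the divisor of the primary endpoint, and divides the per-week incontinence mean by days instead of weeks

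*Combined protocol and SAP*

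**What the plan says.** Section 7.2 calculates urination and incontinence counts "on basis of data recorded by patients into their diaries". The mean daily number of urinations, which is the primary variable, is the diary total "for the study period (between visits) divided into number of days in period". Daily, daytime and nighttime incontinence means are built the same way. The investigator checks the diary at the visit, and the plan is then to "record results in CRF with further automatic calculation of mean values".

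The weekly incontinence variable is defined in the same section: "episodes per week is calculated as total number of episodes during the study period (between visits) divided into number of days in period". It feeds secondary criterion 5 of section 4.1, "Change of mean number of urinary incontinence episodes per week at the 12 week Visit".

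Other sections touch on diary completeness but not on the divisor:

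- Section 4.5.3 asks patients to fill in the diary every day. The baseline diary covers screening: "Screening period should not exceed 14 days before randomization visit/beginning of therapy".
- Section 6.3: "Investigator checks regularity and accuracy of diary filling by the patient", with repeat instruction where needed.
- Section 9.5: "Missing, non-assessable and equivocal data will not be substituted". Its 90% thresholds, like the 95% threshold in 6.3, concern doses taken.

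**The concern.** **Blank days.** The numerator contains only what was recorded, while the divisor is the length of the interval between visits. A day with no entry adds nothing above the line and one day below it, which is the same as entering zero. Section 9.5 says missing data are not substituted, so the two sections must be reconciled. The calculation is automatic, so the formula could be programmed exactly as it stands.

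The primary variable then depends partly on how completely patients fill in diaries. If completeness differs between arms at Week 12, the treatment difference shifts. More blanks in the test arm favour a false finding of non-inferiority; more blanks in the control arm cost power. The documents do not indicate which would occur. The trial is open-label (section 4.3.2), so blinding does not protect equal completeness.

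**Weekly mean.** The weekly formula and the daily formula are identical. Secondary criterion 5 would repeat criterion 1 under a label seven times too large.

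**Working it through.** **Plan's own figure.** With margin 0.8, SD 2.12, one-sided alpha 0.025 and 80% power (section 9.2): n = 2 × 2.12² × (0.84 + 1.96)² / 0.8² = 110.1, so 111 per arm. This reproduces the plan, and the point here does not change it.

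**Inputs.** Section 2.2.6, Table 3 gives a baseline of 11.56 urinations per day and a Week 12 change of −1.65, so the Week 12 level is 11.56 − 1.65 = 9.91. The last interval runs from Day 57 to Day 85, nominally 28 days; baseline is up to 14 days. All blank-day shares below are assumptions.

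**One patient.** One blank day in 28 lowers the Week 12 mean by 9.91/28 = 0.35 per day. A blank share of 0.8/9.91 = 8.1% (about 2.3 days) equals the whole margin. One blank day in 14 lowers baseline by 11.56/14 = 0.83.

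**Change within an arm.** With blank share f at Week 12 and b at baseline, the observed change is 9.91(1 − f) − 11.56(1 − b); the true change is −1.65.

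- 10% at both times: −1.49
- 10% at baseline only: −0.49
- 10% at Week 12 only: −2.64

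Improvement is overstated only when f/b exceeds 11.56/9.91 = 1.17. Equal shares understate it slightly.

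**Non-inferiority test.** SE = 2.12 × √(2/111) = 0.2846. For a true difference d (test minus control) and equal baseline completeness, the observed difference is (9.91 + d)(1 − p_test) − 9.91(1 − p_control). The probability of declaring non-inferiority is Φ((0.8 − observed)/0.2846 − 1.96).

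| Week 12 blank share, test / control | True d | Observed difference | Probability of declaring non-inferiority |
|---|---|---|---|
| 0% / 0% | 0.8 | 0.80 | 2.5% |
| 5% / 5% | 0.8 | 0.76 | 3.4% |
| 10% / 10% | 0.8 | 0.72 | 4.7% |
| 10% / 5% | 0.8 | 0.2245 | 52% |
| 5% / 10% | 0.8 | 1.2555 | 0.02% |
| 1 day in 28 / 0 | 0.8 | 0.4175 | 27% |
| 0% / 0% | 0 | 0 | 80% |
| 5% / 10% | 0 | 0.4955 | 19% |
| 0 / 1 day in 28 | 0 | 0.3539 | 35% |

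Rows with d = 0.8 are type I error; rows with d = 0 are power. The one-day rows mean an average gap of one day across a whole arm.

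**Simulation of the planned ANCOVA.** There were 4,000 runs per setting, with baseline and Week 12 SD 2.81 and correlation 0.715, which gives a change SD of 2.12. The diaries had 14 baseline and 28 Week 12 days. Blank days followed either a common rate or a rate varying between patients, and baseline blanks were 0% or 5%.

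| Quantity | Divisor as written | Recorded-days divisor |
|---|---|---|
| Type I error, 10% / 10% | 5.0–5.9% | 2.1–2.9% over the settings run |
| Type I error, test 10% / control 5% | 50–62% | as above |
| Power at d = 0, test 5% / control 10% | 18–23% | 84–87% over the settings run |
| Power at d = 0, no Week 12 blanks | 81–86% | as above |

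The recorded-days results assume that blank days are unrelated to symptoms.

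**Weekly mean.** For T episodes in D days, the weekly mean is 7T/D. Section 7.2 gives T/D. The Table 3 baseline of 14.53 per week would be reported as 14.53/7 = 2.08.

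**The case against.** The strongest reply is that section 7.2 is ambiguous, not wrong. Read together with the no-substitution rule in 9.5, the days in the period could mean days with data, so a blank day would leave both numerator and divisor. Data queries for missing entries (section 13.1) would reduce blanks. A separate eCRF manual, which is not among the documents, may specify the calculation. The dose-compliance rule may also remove some poor diarists, since doses are logged in the same diary. At a 10% blank rate, about 54% of patients would have three or more blank days in 28, which is below 90% if compliance were judged from the diary over that interval. Finally, the largest error rates need a sustained 5-point imbalance between arms, and nothing in the documents predicts one.

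Part of this stands. The imbalance figures are hypothetical sensitivities, and equal blank shares do only modest harm. The simulations also omit the compliance exclusion. But the favourable reading is not written anywhere, and if it is intended it needs only to be stated. Queries and diary checks can find blanks without saying how those that remain enter the mean. The compliance exclusion is a partial safeguard: tablet counts also feed compliance, both indicators must fall short, and a late gap is diluted over 84 days.

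For the weekly mean, the reply is that the intended unit is clear from section 4.1 and p-values do not change. Both are true, but the formula is still wrong for its label.

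**Conclusion.** Both parts hold and should be fixed before the data are analysed.

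The weekly formula is wrong without any assumption. Its values are one seventh of the labelled unit, and criterion 5 duplicates criterion 1. This is a unit error that leaves between-arm p-values unchanged.

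The missing rule for blank days matters more because it concerns the primary variable. Under the literal reading and the assumed rates, equal Week 12 blanks of 5% to 10% raise type I error to 3.4–4.7% by formula, and to 5.0–5.9% in simulation at 10%. A 5-point imbalance can defeat the test in either direction, and even an average gap of one day in 28 gives a type I error of 27% or power of 35%, depending on the arm. These sizes depend on the assumed blank shares, the Table 3 means, the planned SD and 111 patients per arm. No direction of bias is claimed.

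**What to change.** In section 7.2 and the eCRF derivation:

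- Divide each total by the number of days in the interval with a valid diary record, at baseline and at every visit.
- Set the visit value to missing below a pre-stated minimum number of valid days.
- Make the diary and eCRF distinguish a blank day from a recorded day with zero episodes, which the incontinence endpoints need, and capture the number of valid days if this is not already done.
- Define the weekly incontinence mean as seven times the daily mean, and state that its Week 12 comparison is then the same test as secondary criterion 1 in other units.
- Cross-refer 7.2 and 9.5 so that they give one rule.

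The cost is protocol and SAP wording, one eCRF calculation and possibly one added field; section 7.2 does not show that day-level data are captured. Design and sample size are unchanged. The downside is that a few sparse visits become missing: 0–0.6% of patients in the simulations, with half the days as the minimum. The recorded-days mean also still assumes that blank days resemble recorded ones.

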8 SAFETY ASSESSMENT

8.1 List of safety parameters

- 1) Frequency for development of adverse events (AE) and serious adverse events (SAE).
- 2) Frequency of development of AE and SAE, depending on application of the product.
- 3) Frequency of development of AE and SAE, bringing to treatment cessation/withdrawal from the study.
- 4) Residual urine volume assessment using US-examination of the bladder at the study visits against study start visit.
- 5) Changes of laboratory parameters, ECG parameters and vital parameters assessment.

8.2 Methods, terms of assessment, registration and analysis of safety parameters

8.2.1 Vital parameters assessment:

Vital parameters assessment (systolic and diastolic BP, HR) will be assessed following 5 minutes resting period at the sitting position.

All visits include physical examination with vital parameters assessment

8.2.2 Clinical and laboratory examinations

Total blood count and blood biochemistry and urinalysis will be performed during screening visit, Visit 5 and Visit 6 (see Section 4.5.5.2).

Blood count includes determination of hemoglobin, hematocrit, WBC and full blood count, platelets count.

Blood biochemistry includes determination of ALT, AST, bilirubin, creatinine, total protein, glucose, alkaline phosphatase, cholesterol, potassium, sodium values.

Serological examination will include testing for HIV, hepatitis B and hepatitis C.

Urinalysis includes determination of specific gravity, pH, protein and urea sediment examination.

All assessments will be performed in central laboratory. Total volume of blood, sampled from patients during the study, will be approximately **35 ml**.

Dipstick pregnancy test should be performed for female patients of childbearing potential – during screening visit, before randomization (Visit 2) and after finishing of the therapy (Visit 6).

Investigator should validate results and assess remarks (notes) in laboratory tests prints. In case of deviations clinically significant changes should be emphasized. Investigator should sign and date the laboratory tests prints approving their verified status.

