2.3.1 Expected side effect of the study product [13]

Adverse reactions towards imidafenacin, including deviations of laboratory parameters, were reported in 533 (45.5%) of 1172 studied cases. Primary adverse reactions included: thirst/dry mouth in 368 cases (31.4%), constipation in 98 cases (8.4%), photophobia in 18 cases (1.5%), blurred vision in 16 cases (1.4%), drowsiness in 16 cases (1.4%), gastric discomfort in 13 cases (1.1%), increased triglycerides level in 13 cases (1.1%) and increased activity of gamma-glutamyl transferase (GGT) in 12 cases (1.0%).

In additional clinical trials of dosage and application adverse reactions were reported, including deviations of laboratory parameters, in 215 (49.4%) of 435 studied cases. Primary adverse reactions included: thirst/dry mouth in 164 cases (37.7%), constipation in 59 cases (13.6%), residual urine volume in eight cases (1.8%), leukocyturia in seven cases (1.6%), gastric discomfort in six cases (1.4%), headache in five cases (1.1%) and dysuria in five cases (1.1%).

Clinically significant adverse reactions:

- Acute glaucoma (occurrence rate 0.06%). Because acute glaucoma morbidity rate due to increased intraocular pressure was reported, patients require close monitoring. In case of this event appearance product intake should be stopped and correspondent measures should be undertaken.
- Retention of urine (frequency is not known: based on spontaneous reports). Patients should be under close monitoring due to the risk of urine retention. In case of this event appearance product intake should be stopped and correspondent measures should be undertaken.
- Liver abnormality: increased level of liver enzymes (frequency is not known: based on spontaneous reports). Liver function impairment may present with increased alanine aminotransferase (ALT), aspartate aminotransferase (AST) and bilirubin values. Patients should be closely monitored and in case of any abnormalities appearance product intake should be

stopped and correspondent measures should be undertaken.

Clinically significant adverse reactions (similar products):

- Paralytic intussusceptions: cases of paralytic ileus were reported after administration of similar products (other medicines for OAB treatment), so patients require close monitoring. In case of correspondent symptoms appearance, including constipation and abdominal distension, product intake should be stopped and correspondent measures should be undertaken.

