4.5.3.6 Unplanned visit

If patient prematurely withdraws from the study at any stage, it is required, if possible, to perform all procedures associated to premature withdrawal from the study visit within one week following decision of patient withdrawal. Procedures of this visit are identical to the procedures of the end of treatment visit (Visit 6).

Table 5 Timetable of basic procedures of the study

	Visit 1	Visit 2	Visit 3 (2 weeks ± 3 days)	Visit 4 (4 weeks ± 3 days)	Visit 5 (8 weeks ± 3 days)	Visit 6 (12 weeks ± 3 days)	Visit 7 (30 + 5 days after end of treatment)
Days (D)	D from - 14	D1	D15 (±3)	D29 (±3)	D57 (±3)	D85 (±3)	D114 -
Reception of the informed consent	X						
Demographic data ¹ /patient history acquirement	X						
Previous and concomitant therapy assessment	X	X	X	X	X	X	X
Assessment and registration of AE	X	X	X	X	X	X	X
Physical examination ²	X	X	X	X	X	X	X ³
Complete blood count ⁴	X				X	X	
Blood chemistry ⁵	X				X	X	
Urinalysis ⁶	X				X	X	
Serological examination (HIV, Hep B and C)	X						
PSA level assessment (male only)	X						
Pregnancy test (only women with child-bearing potential)	X	X				X	

US-examination of kidneys, bladder and urine excretory ways (residual urine volume assessment)	X						
US examination of the bladder with residual urine volume assessment		X		X	X	X	
Cough probe	X						
12-lead ECG	X					X	
Assessment with OAB Awareness Tool Questionnaire	X	X	X	X	X	X	
Quality of Life assessment with EQ5D Questionnaire		X				X	
Issue/return and assessment of the diary	X	X	X	X	X	X	
Randomization		X					
Study product issue:		X	X	X	X		
Study product return, compliance assessment			X	X	X	X	

¹ Sex, date of birth, race, body mass, height

²Physical examination includes vital parameters assessment

³Is not conducted in case of telephone contact with the patient

⁴Hemoglobin, hematocrit, white blood cells and differential blood count, platelets.

⁵ ALT, AST, bilirubin, creatinine, total protein, glucose, alkaline phosphatase, cholesterol, potassium, sodium

⁶ Specific gravity, pH, protein, urinary sediment

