4.5.5.2 Laboratory parameters

Following laboratory rests will be performed in central laboratory.

- **Complete blood count:** Hemoglobin, hematocrit, WBC and full blood count, platelets count – during screening, on Week 8 of treatment (Visit 5) and after the end of therapy (Week 12, Visit 6).
- **Blood serum biochemistry:** ALT, AST, bilirubin, creatinine, total protein, alkaline phosphatase, cholesterol, potassium, sodium – at screening on Week 8 (Visit 5) at the end of therapy (week 12, Visit 6). Before blood sampling for biochemical analysis patient should refrain from food and drink only water for, at least, 8 hours.
- **Urinalysis:** Specific gravity, pH, protein, urinary sediment – during screening, on Week 8 of treatment (Visit 5) and after the end of therapy (Week 12, Visit 6).
- **Serological testing for infections:** Blood analysis for presence of antibodies to HIV, antibodies to Hepatitis C virus, Hepatitis B virus (HBsAg) is performed during screening only.
- **Total prostatic specific antigen (PSA) level:** Assessment is performed in all male patients only during screening. Assessment result is used for validation of patient's conformity to inclusion/non-inclusion criteria (PSA exceeding 4 ng/ml is considered to be non-inclusion criteria).

Detailed description of laboratory probes acquirement, handling, storage and shipping, materials (tubes and labels) as well as normal values range of laboratory parameters will be provided in laboratory manual. Laboratory examinations results, performed in central laboratory, will be sent to Investigator by e-mail.

Investigator should validate results and assess remarks (notes) in laboratory tests prints. In case of deviations clinically significant changes should be emphasized. Investigator should sign and date the laboratory tests prints approving their verified status.

Following laboratory rests will be performed in the research center:

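### The scheduled chemistry panel measures neither GGT nor triglycerides, the only two blood-test abnormalities in the protocol's primary adverse-reaction lists for imidafenacin

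*Combined protocol and SAP*

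**What the plan says.** Section 8.2.2 defines the safety chemistry: "Blood biochemistry includes determination of ALT, AST, bilirubin, creatinine, total protein, glucose, alkaline phosphatase, cholesterol, potassium, sodium values". Table 5, footnote 5, gives the same ten analytes: "ALT, AST, bilirubin, creatinine, total protein, glucose, alkaline phosphatase, cholesterol, potassium, sodium". The synopsis and the visit descriptions in Sections 4.5.3.1, 4.5.3.3 (Visit 5) and 4.5.3.4 (Visit 6) repeat them. Section 4.5.5.2 lists nine, leaving out glucose: "ALT, AST, bilirubin, creatinine, total protein, alkaline phosphatase, cholesterol, potassium, sodium". It also requires fasting before the draw: "patient should refrain from food and drink only water for, at least, 8 hours".

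Section 2.3.1 summarises what is known of imidafenacin. In the main data set adverse reactions "were reported in 533 (45.5%) of 1172 studied cases", and the primary reactions end with "increased triglycerides level in 13 cases (1.1%) and increased activity of gamma-glutamyl transferase (GGT) in 12 cases (1.0"%). In further studies of dosage, reactions were reported "in 215 (49.4%) of 435 studied cases", and that list includes "leukocyturia in seven cases (1.6"%). The same section then lists reactions by body system and names both GGT and triglycerides again. It closes with an instruction on study product intake that applies to the reactions listed.

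Section 8.1, item 5, makes change in laboratory parameters a safety criterion. Section 2 states that the trial is meant to show that the two drugs have a comparable safety profile.

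**The concern.** The panel does not match the protocol's own safety profile for the test drug. GGT and triglycerides are the only blood-test abnormalities in the two primary lists of Section 2.3.1, and no version of the panel contains either. Among the four hepatobiliary items listed there (GGT, AST, ALT, bilirubin), GGT is the only one not measured.

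Section 8.3.2 takes adverse events from complaints, interview, examination and laboratory results. A rise in GGT or triglycerides is unlikely to cause a complaint or an examination finding, so with no scheduled test it will normally go unseen. The trial then has nothing to report on either under criterion 5, and any conclusion about comparable safety cannot extend to them.

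There is also an internal mismatch. The closing instruction of Section 2.3.1 depends on reactions that include these two, but the schedule in Section 8.2.2 cannot show whether they have occurred. The instruction speaks of symptoms, so it is unclear whether it reaches laboratory findings at all. The two sections must be reconciled; which rule should apply is not a matter for this point.

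**Working it through.** **1. Panel against reaction lists.**

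| Laboratory finding in Section 2.3.1 | In a primary list? | Measured on schedule? |
|---|---|---|
| Triglycerides raised | Yes, 13/1172 | No |
| GGT raised | Yes, 12/1172 | No |
| Leukocyturia | Yes, 7/435 | Yes, urinary sediment |
| ALT, AST, bilirubin, creatinine, cholesterol raised | No | Yes |
| Lactate dehydrogenase, uric acid raised | No | No |

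**2. The protocol's rates reproduce.** 13/1172 = 1.11% (stated 1.1%); 12/1172 = 1.02% (stated 1.0%); 7/435 = 1.61% (stated 1.6%).

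**3. Expected cases in the imidafenacin arm if both were measured.** Inputs: 150 randomised and 111 completers per arm (Sections 4.2 and 9.2), and the rates above. Expected count = n × p; chance of at least one = 1 − (1 − p)^n.

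| n | Analyte | Expected | At least one | None |
|---|---|---|---|---|
| 150 | Triglycerides | 1.66 | 81% | 19% |
| 150 | GGT | 1.54 | 79% | 21% |
| 111 | Triglycerides | 1.23 | 71% | 29% |
| 111 | GGT | 1.14 | 68% | 32% |

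Each row concerns one analyte alone; none is a joint probability.

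These figures assume that the earlier rates carry over. Section 2.3.1 gives no exposure time for the 1172 cases, and the patient studies in Section 2.2.6 run from 12 to 64 weeks. If the 12-week rates were half as large, the expected counts would be about 0.57 to 0.83. The chance of at least one would then be 43% (GGT, n = 111: 1 − (1 − 0.00512)^111) to 57% (triglycerides, n = 150: 1 − (1 − 0.00555)^150).

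**4. Power to compare event rates.** Take 1.11% against 0% with 150 per arm, the most favourable comparator rate. Fisher's exact test at 0.05 two-sided needs 6 against 0: 5 against 0 gives p = 0.060 and 6 against 0 gives p = 0.030. With 1.66 cases expected, the probability of 6 or more is about 0.7%.

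**5. Continuous values.** Section 9.9 summarises laboratory values and tests them within each arm by paired methods. By the normal approximation, the mean change detectable with 80% power at 0.05 two-sided is (1.96 + 0.84)/√n standard deviations of the change: 2.80/√150 = 0.23 and 2.80/√111 = 0.27. If the arms were compared directly, it would be 2.80 × √(2/n): 0.32 and 0.38. This is where measurement would add information.

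**The case against.** The case for leaving the panel alone is that little is lost. At about 1%, the trial would see one or two cases of each, might well see none, and could not compare the arms on event rates. Neighbouring markers are measured, and the primary endpoint and the other safety criteria are unaffected. Lactate dehydrogenase and uric acid are also listed and unmeasured, so a panel need not contain every listed analyte. All of this stands and sets the severity. It does not remove the mismatch, because GGT and triglycerides, unlike those two, are in a primary list, and because the continuous summaries would be informative where case counts are not.

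Three stronger readings are tempting and should not be adopted.

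- A reader might infer that both effects will be reported as absent and so wrongly support comparable safety. The documents do not say so. Section 9.9 summarises what was collected; an analyte never assayed has no row and no zero. It is unassessed, and would be read as absent only if the report failed to say it was not tested. A locally ordered test could still reveal a case.
- A reader might call these the two most frequent laboratory reactions. Leukocyturia, at 1.6% in the 435-case list, is more frequent, and urinalysis covers it.
- A reader might say that the close monitoring of liver abnormality in Section 2.3.1 is not provided for. That text names ALT, AST and bilirubin, and all three are in the panel.

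**Conclusion.** The point holds as a minor gap in the safety description. GGT and triglycerides are absent from every statement of the panel although Section 2.3.1 treats both as primary reactions, so the trial cannot describe or compare them. This part rests on the text alone.

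The size rests on two assumptions: that the 1172-case rates apply to 12 weeks of treatment with two post-baseline draws, and that cases would be counted as they were in those data. Section 8.3.1 counts a laboratory deviation as an adverse event only if it is clinically significant; the earlier threshold is not given. On those assumptions, about 1.1 to 1.7 cases of each would be expected in 111 to 150 imidafenacin patients. The gain from measuring them is descriptive, mainly through continuous change.

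**What to change.** Add GGT and triglycerides to the central-laboratory chemistry at screening, Visit 5 and Visit 6. Make the change wherever the panel is stated: the synopsis, Sections 4.5.3.1, 4.5.3.3, 4.5.3.4 and 4.5.5.2, Table 5 footnote 5, and Section 8.2.2. Include both in the Section 9.9 summaries of values and changes, by arm. The same amendment can settle whether glucose belongs in Section 4.5.5.2, and should reconcile the closing instruction of Section 2.3.1 with what the schedule measures.

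The cost is a small laboratory fee and the amendment. Blood is already drawn after a fast of at least 8 hours, so no visit, procedure or new preparation is needed. Tube volume should be checked against the laboratory manual, which is not part of these documents.

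If the assays are not added, the clinical study report should state that GGT and triglycerides were not assessed and that no safety conclusion covers them.
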